6.2 On therapy evaluations (see schedule of events Appendix A)

From cycle 1 to 6 (+/- 5-day window):

Prior to each cycle, the following assessments will be completed. If the assessments have been already performed within 5 days of the study drug initiation as a part of screening or baseline evaluations, the study team can decide whether these assessments may or may not be repeated.

- Interval History
- ECOG performance status evaluation
- Physical exam
- Concomitant medication review
- CBC with differential
- Acute Care Panel (Na, K, Cl, CO₂, Creatinine, Glucose, and Urea Nitrogen)
- Mineral Panel (Phosphorus, Magnesium, Albumin, and Calcium)
- Total Protein, Uric Acid, and LDH
- Hepatic Panel (Alk Phosphatase, ALT, AST, Total Bilirubin, and Direct Bilirubin)
- Reticulocyte count
- Beta-2 microglobulin (B2M)
- Direct antiglobulin test (DAT)
- For females of childbearing potential, repeat pregnancy test
- Research blood (up to 80ml)

Additional blood draws, procedures, or imaging include (+/- 5-day window, except for CT scan and bone marrow biopsy):

Cycle 3&4

- Prior to Cycle 3 (within day -14 to 0): Lymphocyte phenotyping (T, B, NK), CT of neck/chest/abdomen/pelvis
- Cycle 3&4 Day 5 (+/- 5 days): Research blood (up to 80ml, optional)
- Cycle 3&4 Day 14, and 22 (+/- 5 days): CBC with differential (may be performed outside of NIH), research blood (up to 80ml) (if the blood was drawn at the NIH)

Cycle 5

- Cycle 5 Day 1 (+/-5-day window): Lymphocyte phenotyping (T, B, NK)

Others

- Up to 3 lymph node biopsies may be obtained for research at any time during therapy (optional, with at least 4 weeks between biopsies).

After cycle 6 (+/- 14-day window):

Following assessments will be done every 3 months while on therapy until disease progression or intolerable side effects.

- Interval History
- ECOG performance status evaluation

- Physical exam
- Concomitant medication review
- CBC with differential
- Acute Care Panel (Na, K, Cl, CO₂, Creatinine, Glucose, and Urea Nitrogen)
- Mineral Panel (Phosphorus, Magnesium, Albumin, and Calcium)
- Total Protein, Uric Acid, and LDH
- Hepatic Panel (Alk Phosphatase, ALT, AST, Total Bilirubin, and Direct Bilirubin)
- Reticulocyte count
- Beta-2 microglobulin (B2M)
- Direct antiglobulin test (DAT)
- For females of childbearing potential, repeat pregnancy test
- Research blood (up to 80ml)

6.3 Response assessment (see schedule of events Appendix A) (+/- 30-day window)

Response assessment will be performed after 6 cycles, and annually (at the anniversary date of the first dose of study drug).

- Interval History
- ECOG performance status evaluation
- Physical exam
- Concomitant medication review
- CBC with differential
- Acute Care Panel (Na, K, Cl, CO₂, Creatinine, Glucose, and Urea Nitrogen)
- Mineral Panel (Phosphorus, Magnesium, Albumin, and Calcium)
- Total Protein, Uric Acid, and LDH
- Hepatic Panel (Alk Phosphatase, ALT, AST, Total Bilirubin, and Direct Bilirubin)
- Reticulocyte count
- Coagulation panel (PT, PTT)
- Serum free light chains, quantitative immunoglobulins
- Beta-2 microglobulin (B2M)
- Haptoglobin
- Direct antiglobulin test (DAT)
- For females of childbearing potential, pregnancy test
- Lymphocyte phenotyping (T, B, NK)
- Flow cytometry panel (optional)
- CT of the neck, chest, abdomen and pelvis. IV and PO contrast will be used unless the patient has a contrast allergy or impaired renal function.
- Bone marrow biopsy after 6 cycles (mandatory). May also obtain annually starting at the anniversary date of the first dose of the study drug (optional). After 1 year on study, bone marrow biopsy and aspirate may be performed 3 months ± 15-days after the patient met CT criteria and hematologic criteria for complete response (optional).
- EKG if medically indicated
- Lymphapheresis for research (optional)
- Lymph node biopsy for research if the patient is willing and has an accessible lymph node. Up to 3 lymph node biopsies may be obtained for research at any time during therapy (optional, with at least 4 weeks between biopsies).
- Research blood (up to 80ml)

6.4 At progression evaluation (see schedule of events Appendix A)

All response assessments as listed in 6.3 may be performed at progression. Additional optional studies may be performed which includes the following:

- Serum protein electrophoresis with immunofixation (SPEP)
- C-reactive protein (CRP)
- PET/CT of the neck, chest, abdomen and pelvis. IV and PO contrast will be used unless the patient has a contrast allergy or impaired renal function
- Peripheral blood interphase FISH with FISH panel containing probes for *ATM* (11q22.3), *D12Z3* (12cen), *D13S319* (13q14.3), *LAMP1* (13q34) and *TP53* (17p13.1)
- IGHV mutational analysis

7.0 CRITERIA FOR RESPONSE

Responses for spleen and lymphadenopathy will be assessed using CT scan scans. In the absence of a CT scan assessment by physical exam may be substituted. Response assessments will be made by IWCLL 2018 guidelines.⁷⁷ Response includes complete response, partial response, and partial response with lymphocytosis (Table 4).

Table 4. Criteria of response

Response	CR	PR ^F	PRL ^F	PD ^G
Group A				
Lymphadenopathy ^A	None >1.5cm	Decrease ≥ 50%	Decrease ≥ 50%	Increase ≥ 50% or any new lesion > 1.5cm
Splenomegaly/ Hepatomegaly ^B	None	Decrease ≥ 50%	Decrease ≥ 50%	Increase ≥ 50% or any new splenomegaly
Blood lymphocytes ^C	< 4000/μL	Decrease ≥ 50% from baseline	Increase or <50% decrease over baseline	Increase ≥ 50% over baseline or > 5000/μL
Bone marrow ^D	Normocellular, <30% lymphocytes, no B-lymphoid nodules	Not applicable	Not applicable	Not applicable
Group B^E				
Platelet count	>100,000/μL	> 100,000/μL or increase ≥ 50% over baseline	> 100,000/μL or increase ≥ 50% over baseline	Decrease ≥ 50% from baseline secondary to CLL
Hemoglobin	> 11.0g/dL	> 11.0 g/dL or increase ≥ 50% over baseline	> 11.0 g/dL or increase ≥ 50% over baseline	Decrease ≥ 50% from baseline secondary to CLL
Neutrophils	> 1500/μL	> 1500/μL or increase ≥ 50% over baseline	Not applicable	Not applicable

CR = complete response; CRi = CR with incomplete blood count recovery; CT = computed tomography; PD = progressive disease; PR = partial response; PRL = partial response with lymphocytosis

Footnotes

^A Sum of the product (SPDs) of up to 6 lymph nodes as evaluated by CT scans. If CT is unavailable, the absence of enlarged lymph nodes (> 1.5cm) documented by physical exam is acceptable.

^B Splenomegaly assessed by CT scan. In the absence of a CT scan assessment by physical exam may be substituted. New splenomegaly or hepatomegaly is assessed by physical exam.

^C Patients with treatment-related lymphocytosis remain on study unless associated with other signs of progressive disease. Treatment-related lymphocytosis may occur at the start of treatment or at any time when resuming treatment after a dose interruption.

^D Complete response requires confirmation with bone marrow biopsy. In the absence of a confirmatory bone marrow biopsy the response can be classified as CRu. In case of a hypocellular marrow the response can be classified as CRi.

^E PR or PRL, at least one Group B criterion has to be met. CR, all criteria in A and B must be met. In subjects meeting Group A criteria for CR but not Group B, the response can be classified as CRi.

^F PR and PRL criteria refer to changes from baseline.

^G PD criteria refer to changes from baseline in subjects who never responded and to changes from best response (nadir) in subjects who responded.

Complete Response (CR)

- Is defined as meeting all criteria in A and B.
- Meet all criteria in A and B but bone marrow confirmation is pending: unconfirmed complete response (CRu).
- Meet all criteria in A but bone marrow is hypocellular, or criteria in B are not met: complete response with incomplete blood count recovery (CRi).

Partial Response (PR)

- Is defined by 2 criteria in Group A if abnormal before therapy and at least 1 Group B criterion.
- In subjects with just 1 involved Group A site (e.g., lymphadenopathy in a subject with SLL), the response is PR when the criterion for that site is met.
- If criteria for PR, except for a decrease in the number of blood lymphocytes by 50% or more from the value before therapy, are met, then assessment will be PRL.
- SLL subjects need to have both ALC >50% and ALC >5k to be PRL.

Progressive Disease (PD)

Progressive disease is defined by:

- Progressive lymphocytosis $\geq 50\%$ from nadir, confirmed due to expansion of CLL cells by flow cytometry ($\geq 5,000$ B lymphocytes/ μL).
- or an increase $\geq 50\%$ in the sum of the products of at least two lymph nodes with at least one lymph node > 1.5 cm in greatest diameter,
- or the appearance of a new pathologic lymph node > 1.5 cm in greatest diameter,
- or new onset splenomegaly or hepatomegaly on physical exam, or other new CLL organ infiltrates,
- or an increase $\geq 50\%$ in splenomegaly or hepatomegaly when occurring in the absence of a confounding process (e.g., infection), and that is maintained or continues to progress over a period of at least 3 months.

Other criteria for PD include:

- Transformation to a more aggressive histology (e.g., Richter syndrome). Whenever possible, this diagnosis should be established by lymph node biopsy.
- The progression or development of cytopenia (excluding autoimmune cytopenia), as documented by a decrease of hemoglobin levels by > 2 g/dL, or by a decrease of platelet counts by $> 50\%$, that persists for at least 3 months defines disease progression if a marrow biopsy supports a disease related etiology.

A rise of the lymphocyte count at the beginning of therapy or resumption of therapy after a period of drug hold in absence of other indications of progressive disease will not be considered as evidence of progressive disease because this type of agent does typically lead to a mobilization of tumor cells into the peripheral blood.

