Unexpected adverse reaction: An adverse event or suspected adverse reaction is considered “unexpected” if it is not listed in the investigator brochure or is not listed at the specificity or severity that has been observed; or, if an investigator brochure is not required or available, is not consistent with the risk information described in the general investigational plan or elsewhere in the current application. “Unexpected”, also refers to adverse events or suspected adverse reactions that are mentioned in the investigator brochure as occurring with a class of drugs or as anticipated from the pharmacological properties of the drug, but are not specifically mentioned as occurring with the particular drug under investigation.

Unanticipated Problem (UP): Any incident, experience, or outcome that meets all of the following criteria:

1. **unexpected** in terms of nature, severity, or frequency in relation to
 - a. the research risks that are described in the IRB-approved research protocol and informed consent document; Investigator’s Brochure or other study documents; and
 - b. the characteristics of the subject population being studied; and
2. **related or possibly related** to participation in the research; and
3. places subjects or others at a **greater risk of harm** (including physical, psychological, economic, or social harm) than was previously known or recognized.

Unanticipated Problem that is not an Adverse Event: An unanticipated problem that does not fit the definition of an adverse event, but which may, in the opinion of the investigator, involves risk to the subject, affect others in the research study, or significantly impact the integrity of research data. For example, report occurrences of breaches of confidentiality, accidental destruction of study records, or unaccounted-for study drug.

Asymptomatic Treatment-related Lymphocytosis: This event should also not be considered an AE. Subjects with treatment-related lymphocytosis should remain on study treatment and continue with all study-related procedures.

Protocol Deviation (PD): Any change, divergence, or departure from the IRB approved research protocol.

Non-compliance: The failure to comply with applicable NIH HRPP policies, IRB requirements, or regulatory requirements for the protection of human research. Noncompliance may be further characterized as:

1. **Serious non-compliance:** Non-compliance that:
 - a. Increases risks, or causes harm, to participants

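### Table 4's progression column conflicts with the written progression criteria in Section 7.0, chiefly for lymphocytes and haemoglobin, and Section 5.5.3 cites a Section 7.3 that does not exist

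*Combined protocol and SAP*

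**What the plan says.** Section 7.0 holds two sets of PD criteria.

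- **Table 4, PD column.** Lymphocytes: an increase of at least 50% "over baseline or > 5000"/µL. Haemoglobin and platelets: each a fall of at least 50% attributed to CLL. Spleen and liver: an increase of at least 50%, or new splenomegaly. Footnote G sets the reference value: "PD criteria refer to changes from baseline in subjects who never responded and to changes from best response (nadir) in subjects who responded".
- **Written criteria, introduced by "Progressive disease is defined by".** Lymphocytes: a rise of at least 50% "from nadir, confirmed due to expansion of CLL cells by flow cytometry", with at least 5,000 B lymphocytes/µL. Cytopenia: a haemoglobin fall of more than 2 g/dL or a platelet fall of more than 50%, lasting at least 3 months and supported by marrow biopsy. Spleen or liver increase of at least 50%: only without a confounding process and when sustained for at least 3 months.

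Section 5.5.3 lists PD among the reasons for permanent discontinuation and refers to Section 7.3 for its definition. Section 7.0 has no numbered subsections, in the body or in the table of contents. Section 9.2 lists PFS and duration of response as secondary endpoints, and Section 9 gives no progression definition of its own.

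**The concern.** The same patient data can be progression under one statement and not under the other. For lymphocytes the table joins two conditions as alternatives where the text requires both. For haemoglobin the required size of fall is much larger in the table than in the text. The table therefore cannot be read simply as a shorthand for the text, because it is looser on one row and tighter on another.

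At stake are the progression date used for PFS and for the end of response, and the decision to stop ibrutinib. Section 5.5.3 is the place where a reader would look to learn which definition controls treatment, and its reference leads nowhere.

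**Working it through.** The plan gives no figure to reproduce on this point. The two rules are set side by side below. Nadirs and haemoglobin reference values are illustrative assumptions, because the protocol states none.

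**1. Lymphocytes, charitable reading.** Take a responder with nadir N at or below 5,000/µL and a later, higher count C. Apply footnote G (change measured from nadir), read the table's 5,000 as a rise across that level, and count all lymphocytes as flow-confirmed CLL B cells. That last assumption favours agreement.

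- Table cell met: C ≥ 1.5N **or** C > 5,000.
- Text met: C ≥ 1.5N **and** C ≥ 5,000.

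| Nadir N (/µL) | Table cell first met | Text first met | Counts meeting the table cell only |
|---|---|---|---|
| 500 | 750 | 5,000 | 750–4,999 |
| 1,000 | 1,500 | 5,000 | 1,500–4,999 |
| 2,000 | 3,000 | 5,000 | 3,000–4,999 |
| 3,000 | 4,500 | 5,000 | 4,500–4,999 |
| 4,000 | 5,001 | 6,000 | 5,001–5,999 |
| 4,500 | 5,001 | 6,750 | 5,001–6,749 |

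Within this range the rules agree only where 1.5N = 5,000, that is N ≈ 3,333. Elsewhere the table is broader. Two examples:

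- 1,000 to 1,600 is a 60% rise. It meets the cell and fails the text because 1,600 < 5,000.
- 4,500 to 5,100 is a rise of 600/4,500 = 13.3%. It meets the cell and fails the text because it is under 50%.

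The table's own CR limit for lymphocytes is below 4,000/µL. When 1.5N < 4,000, so N < 2,667, some counts satisfy both the CR and the PD lymphocyte cells (1,500 to 3,999 for N = 1,000).

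**2. Nadirs above 5,000/µL.** No rise across 5,000 is possible, so the table reduces to C ≥ 1.5N. The text's 5,000 condition is then met automatically if all lymphocytes are B cells. On that assumption the rules coincide.

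**3. Lymphocytes, literal reading.** A fall from 100,000 to a stable 40,000/µL is a 60% decrease and meets the PR lymphocyte cell. It also exceeds 5,000/µL and so meets the PD cell. It is not PD under the text, since there is no rise from nadir.

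**4. Haemoglobin.** With reference value h, the text threshold is below h − 2 and the table threshold is h/2 or lower. The gap is (h − 2) − h/2 = h/2 − 2.

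| h (g/dL) | Text: below | Table: at or below | Gap (g/dL) |
|---|---|---|---|
| 9 | 7.0 | 4.5 | 2.5 |
| 11 | 9.0 | 5.5 | 3.5 |
| 13 | 11.0 | 6.5 | 4.5 |

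A sustained, marrow-supported fall into the gap is PD by the text but does not meet the table cell.

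**5. Platelets and spleen/liver.** The platelet cut-offs differ only at exactly 50%. What the table omits is the 3-month persistence for both rows, marrow support for platelets, and absence of a confounder for spleen/liver. Three months is about one visit interval after cycle 6 (Section 6.2).

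**6. Weight of one event.** With 27 to 32 subjects (Section 9.3) all at risk, one reclassified progression moves a Kaplan-Meier curve by 1/32 = 3.1 to 1/27 = 3.7 percentage points.

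**The case against.** The strongest reply is that the text is identifiably the definition. It has its own PD heading and defining sentence, while Table 4 is introduced as a table of response categories. Footnote E says how to combine the cells for CR, PR and PRL but not for PD, so meeting one PD cell is not expressly progression. Elsewhere (the SLL rule for PRL in Section 7.0, the lymphocytosis description in Section 11.2.1) the 50% and 5,000 conditions are joined by 'and', so the table's 'or' looks like a slip. The platelet and spleen/liver cells can pass as summaries, and the intended target of the Section 7.3 reference is plain. The endpoints concerned are descriptive. If the 96% 30-month PFS cited in Section 2.6.2 for frontline ibrutinib held here, only about 27 × 0.04 = 1.1 events would be expected by then.

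Most of this stands and limits the weight of the point. It does not remove it: the table has its own PD column and its own PD footnote, and no sentence subordinates it to the text.

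Three stronger readings are tempting and not supported:

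- A reader might infer that the lymphocyte rules differ for every responder, with the table always broader. They coincide above a nadir of 5,000/µL under the stated assumption. PR needs only a 50% fall, so nadirs above that level are possible.
- A reader might infer that ibrutinib's usual lymphocytosis would count as progression. Footnote C ("Patients with treatment-related lymphocytosis remain on study unless associated with other signs of progressive disease"), the closing paragraph of Section 7.0 ("A rise of the lymphocyte count at the beginning of therapy or resumption of therapy after a period of drug hold") and Section 10.1 ("Subjects with treatment-related lymphocytosis should remain on study treatment") exclude it. They do not cover a later low-level rise in a responder on uninterrupted drug.
- A reader might infer that the primary result is at risk. PD does not enter the CR count, and the primary safety endpoint counts discontinuation for intolerable side effects only.

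**Conclusion.** The conflict is real and should be corrected. It is substantive for lymphocytes at nadirs of 5,000/µL or less (other than near 3,333/µL) and for haemoglobin. It is mainly a matter of missing qualifiers for platelets and spleen/liver. The written criteria appear to be the operative definition, but the protocol does not say that they govern, and the one cross-reference that could settle it is broken.

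The consequences fall on secondary PFS, duration of response and PD-based discontinuation. Section 9.7 softens the last by letting the PI continue ibrutinib after progression in selected cases. The primary CR endpoint, the primary safety endpoint and the sample size are unaffected. How many subjects would be reclassified cannot be estimated from the documents; it is probably small. The lymphocyte ranges rest on assumed nadirs, footnote G, the charitable reading of the 5,000 limit, and all lymphocytes being B cells.

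**What to change.** - **Lymphocyte PD cell:** increase of at least 50% from nadir AND at least 5,000 B lymphocytes/µL, flow-confirmed, excluding treatment-related lymphocytosis.
- **Haemoglobin PD cell:** fall of more than 2 g/dL, lasting at least 3 months, marrow-supported.
- **Platelet PD cell:** add 3-month persistence and marrow support.
- **Spleen/liver PD cell:** for the 50% increase, add absence of a confounding process and 3-month persistence.
- **Section 5.5.3:** refer to the written PD criteria in Section 7.0 and state that they govern over Table 4.

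The cost is protocol wording only. The text already requires the confirmatory steps, and the flow panel is already listed in Section 6.3 (as optional) and in Appendix A.

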5.6 Supportive Care (non-investigational)

5.6.1 Blood Products: Patients will be transfused packed red blood cells and platelets as clinically indicated. All required blood products will be irradiated prior to transfusion.

5.6.2 Growth Factors: Filgrastim or peg-filgrastim may be used to accelerate count if ANC < 500/uL at the PI's discretion, for example, for febrile neutropenia.

5.6.3 Anti-infective agents will be used as indicated for treatment of intercurrent infections.

5.6.4 PCP prophylaxis: Sulfamethoxazole/trimethoprim DS PO once daily 3 times per week (or alternative agent in case of sulfa allergy) from cycle 1 to 9 and beyond, at the discretion of the PI. Patients who may be at an increased risk of PCP infection include those who are taking long-term

high-dose steroids or immune suppressants, and those who had prior PCP infection. Patients allergic to sulfa drugs who are deemed appropriate for prophylaxis may be given an alternative agent at the discretion of the PI.

5.6.5 Anti-viral prophylaxis: Acyclovir 800 mg PO twice daily or valacyclovir 500mg PO once daily may be used the discretion of the PI (not obligatory).

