9.0 BIOSTATISTICAL CONSIDERATIONS

9.1 Primary endpoint:

Primary efficacy endpoint is the rate of complete response at 24 weeks or after 6 cycles. Response to treatment will be determined according to IWCLL 2008 criteria incorporating 2012 and 2013 clarifications pertaining to patients treated with kinase inhibitors.

Primary safety endpoint is the rate of treatment discontinuation within the first 24 weeks or 6 cycles due to intolerable side effects.

9.2 Secondary endpoints:

- Progression-free survival (PFS)
- Overall survival (OS)
- Best response during treatment
- Duration of response
- Minimal residual disease (MRD) state defined by flow cytometry
- Clonal dynamics on treatment assessed using interphase FISH and gene sequencing for somatic mutations
- Shifts in cellular and humoral immunity on treatment (e.g. immunoglobulin levels, myeloid-derived stromal cells, B-cell repertoire, T-cell subsets including regulatory T cells, T helper 1, T helper 2, T helper 17)
- Expression of checkpoint inhibitory molecules such as PD-L1, PD-1, and CTLA-4

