9.3 Sample size

The study will enroll 27 evaluable subjects for response assessment for primary efficacy and safety endpoints. Up to 5 additional subjects may be enrolled to account for early discontinuation before completing 6 cycles due to non-treatment related reasons. Those subjects with non-treatment related early discontinuation will not be evaluable for the primary efficacy and safety endpoints.

As for the primary efficacy endpoint, CR with ibrutinib alone has been reported to be 13% in previously untreated CLL population,⁵⁶ and 0-2% in relapsed/refractory CLL.^{54,55} When ibrutinib and rituximab were combined in high-risk CLL patients, CR rate was 8%.⁶¹ Based on the reported data, a CR rate exceeding 20% would generate an interest for further studies. We will use a Simon's minimax two-stage design to test the null hypothesis (H_0) that the CR rate in the study is $\leq 5\%$ against the alternative hypothesis (H_1) that it is $>5\%$ with type I error of 0.05. If the true CR rate is 20%, the study using the following two-stage design has 80% power. In the first stage, we will enroll 13 subjects and assess CR rate after 6 cycles. If there is no CR in these 13 subjects, we will stop the study; if 1 or more CRs are observed, we will enter an additional 14 subjects for a total of 27 evaluable subjects. The null hypothesis will be rejected if 4 or more CRs are observed in 27 subjects. Early discontinuation within the first 24 weeks or 6 cycles due to toxicity related to study drug are counted as non-response towards the primary efficacy endpoint.

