10.1.1 Severity

Definitions found in the Common Terminology Criteria for Adverse Events version 4.03 (CTCAE v4.03) will be used for grading the *severity* (intensity) of **non-hematologic** AEs:

Grade 1 (Mild AE) – experiences which are usually transient, requiring no special treatment, and not interfering with the patient’s daily activities

Grade 2 (Moderate AE) – experiences which introduce some level of inconvenience or concern to the patient, and which may interfere with daily activities, but are usually ameliorated by simple therapeutic measures

Grade 3 (Severe AE) – experiences which are unacceptable or intolerable, significantly interrupt the patient’s usual daily activity, and require systemic drug therapy or other treatment

Grade 4 (Life-threatening or disabling AE) – experiences which cause the patient to be in imminent danger of death

Grade 5 (Death related to AE) – experiences which result in patient death

Grading Scale for Hematologic Toxicity in CLL [Hallek 2008]

Grade ¹	Decrease in platelets ² or Hb ³ (nadir) from pretreatment value	Absolute neutrophil count/ μ L ⁴ (nadir)
0	No change to 10%	≥ 2000
1	11%-24%	≥ 1500 and < 2000
2	25%-49%	≥ 1000 and < 1500
3	50%-74%	≥ 500 and < 1000
4	$\geq 75\%$	< 500

1. Grades: 1, mild; 2, moderate; 3, severe; 4, life-threatening; 5, fatal. Death occurring as a result of toxicity at any level of decrease from pretreatment will be reported as Grade 5.
2. Platelet counts must be below normal levels for Grades 1 to 4. If, at any level of decrease, the platelet count is $< 20 \times 10^9/L$ (20,000/ μ L), this will be considered Grade 4 toxicity, unless a severe or life-threatening decrease in the initial platelet count (eg, $< 20 \times 10^9/L$ [20,000/ μ L]) was present pretreatment, in which case the patient is not evaluable for toxicity referable to platelet counts.
3. Hemoglobin (Hb) levels must be below normal levels for Grades 1 to 4. Baseline and subsequent Hb determinations must be performed before any given transfusions. The use of erythropoietin is irrelevant for the grading of toxicity, but should be documented.

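### A complete response for the primary endpoint can be scored on physical exam when CT is missing, and the 4-of-27 cut-off has little room for one such error

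*Combined protocol and SAP*

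**What the plan says.** - **Endpoint.** Section 9.1: "Primary efficacy endpoint is the rate of complete response at 24 weeks or after 6 cycles".
- **Test.** Section 9.3 uses a Simon minimax two-stage design with a null CR rate of 5% or less, "with type I error of 0.05". It stops at 0 CRs among 13 subjects and otherwise continues to 27, rejecting at 4 or more CRs. On power: "If the true CR rate is 20%, the study using the following two-stage design has 80% power".
- **Nodal criterion for CR.** Table 4 requires that no node exceed 1.5 cm. Footnote A adds: "If CT is unavailable, the absence of enlarged lymph nodes (> 1.5cm) documented by physical exam is acceptable". The opening of section 7.0 and footnote B let exam stand in for CT for the spleen as well.
- **Schedule.** Section 6.3 lists CT of neck, chest, abdomen and pelvis at the post-cycle-6 assessment without marking it optional, in a window of 30 days either side. Marrow biopsy is mandatory at that visit.
- **CR, CRu and CRi.** CR needs every Group A and Group B criterion, and footnote D requires marrow confirmation. CRu (marrow pending or absent) and CRi (hypocellular marrow or unrecovered counts) stand under the same heading as CR, with their own labels. Sections 9.1 and 9.3 mention neither.

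**The concern.** Disease at entry is mapped by CT of four regions. Palpation cannot show that a mediastinal or retroperitoneal node seen on that scan has shrunk to 1.5 cm or less. The condition that footnote A accepts on exam is the nodal CR criterion itself, so the fallback reaches CR and not only partial response (PR). For deep nodes the error runs one way: exam can miss residual disease and turn a PR into a CR.

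The trial is single-arm and open-label, and the documents describe no independent review of response. Section 9.3 counts early discontinuation for drug toxicity as non-response, but no rule says how a missing CT bears on the primary endpoint. The only text that applies is the substitution, which resolves the case in favour of CR. At stake is whether a result of 4 CRs in 27 supports rejecting a 5% rate.

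**Working it through.** **Inputs from section 9.3:** null rate 0.05; alternative 0.20; 13 subjects in stage 1, stopping at 0 CRs; 14 more in stage 2; reject at 4 or more of 27. The number of false CRs and the share of true CRs without CT are not in the documents. Both are assumptions below.

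**1. The plan's own figures.** With b(x; 13, p) the binomial probability of x CRs in stage 1,

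R(p) = Σ over x = 1 to 13 of b(x; 13, p) × P[Bin(14, p) ≥ max(0, 4 − x)].

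| Stage 1 CRs | p = 0.05 | p = 0.20 |
|---|---|---|
| 1 | 0.35123 × 0.03005 = 0.01056 | 0.17867 × 0.55195 = 0.09862 |
| 2 | 0.11092 × 0.15299 = 0.01697 | 0.26801 × 0.80209 = 0.21496 |
| 3 | 0.02140 × 0.51233 = 0.01097 | 0.24567 × 0.95602 = 0.23487 |
| 4 or more | 0.00310 | 0.25268 |
| **R(p)** | **0.0416** | **0.801** |

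The stated design reproduces: type I error is below 0.05 and power is 80%.

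**2. One false CR, the other 26 subjects at 5%.**
- *In stage 1.* The false CR alone passes the 1-of-13 gate. Rejection then needs 3 or more CRs among 26: 1 − 0.26352 − 0.36061 − 0.23724 = 0.1386.
- *In stage 2.* Stage 1 must still yield a CR by itself, so subtract P(0 of 13) × P(3 or more of 13) = 0.51334 × 0.02451 = 0.01258. This gives 0.13863 − 0.01258 = 0.1261.

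Either is about three times 0.0416 (ratios 3.3 and 3.0).

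**3. A false-CR rate f among true non-CR subjects.** The scored rate is 0.05 + 0.95f, and the expected number of false CRs is 27 × 0.95 × f.

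| f (assumed) | Scored rate | Expected false CRs in 27 | Chance of rejection |
|---|---|---|---|
| 0 | 0.0500 | 0 | 0.042 |
| 1% | 0.0595 | 0.26 | 0.070 |
| 2% | 0.0690 | 0.51 | 0.107 |
| 3% | 0.0785 | 0.77 | 0.151 |

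The nominal 0.05 is passed at f of about 0.33%.

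**4. Cost of requiring CT.** If a share m of true CRs lack CT and count as non-CR, the scored rate at the alternative is 0.20 × (1 − m). For m = 5%, R(0.19) = 0.765. For m = 10%, R(0.18) = 0.724.

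**The case against.** **The route is narrow.** CT is the stated method and exam is only a fallback. The scan is scheduled, the window is wide, CT from outside institutions is accepted (section 6.0), and contrast allergy or renal impairment removes the contrast rather than the scan. Exam alone does not make a CR: marrow, blood lymphocytes and all three counts must also qualify. All of this stands and limits how often the problem can arise. It does not close the gap, because marrow and blood say nothing about the size of a deep node.

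**The size is conditional.** The 13–14% supposes that a false CR has occurred, so it is not the design's type I error. Any 4-of-27 rule would be as sensitive to misclassification from any source. That is right. The calculation shows how little slack there is, not that inflation will happen.

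**Stronger readings that a reader might infer.**
- *CRu and CRi count as CR because they share its heading.* The text does not support this. CR is defined strictly and the other two carry separate definitions. What is missing is a sentence in 9.1 or 9.3 that excludes them.
- *Transfused or growth-factor-supported counts may qualify as CR.* Section 5.6 says "Patients will be transfused packed red blood cells and platelets as clinically indicated" and allows filgrastim at low neutrophil counts, while Table 4 sets no condition on support. That is silence, not permission, and the guideline adopted by reference may cover it, which cannot be checked here. On schedule the last fludarabine dose (cycle 4, day 5) is 23 + 28 + 28 = 79 days, about 11 weeks, before the end of cycle 6, which weakens the idea that drug-suppressed counts crowd the CR/CRi boundary at the assessment.
- *The protocol guards against supported counts in toxicity grading but not in response.* Section 10.1.1 does say "Baseline and subsequent Hb determinations must be performed before any given transfusions", but its notes also treat erythropoietin and G-CSF use as having no bearing on the grade. The contrast fails.

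**Conclusion.** The concern holds for the CT substitution. Followed as written, section 7.0 can score a subject with residual deep nodes as a CR for the primary endpoint. One such subject at a true rate of 5% lifts the chance of rejection from 4.2% to 12.6% or 13.9%, depending on the stage in which it falls. That rests on an assumed single case; the documents give no frequency of exam-only assessments, and the schedule suggests that they will be few. The sample size, stage 1 rule and cut-off are correct as stated and need no change.

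The standing of CRu and CRi in the 4-of-27 count is a smaller gap in 9.1 and 9.3, suited to the same amendment. Whether counts must be unsupported is an open question, tied to section 7.0 naming IWCLL 2018 while section 9.1 names IWCLL 2008 with the 2012 and 2013 clarifications.

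**What to change.** Add to section 9.1, with a matching line in Table 4 footnotes A and B:

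> For the primary endpoint and the efficacy test in section 9.3, CR requires a CT at the post-cycle-6 assessment (within its ±30-day window) and marrow confirmation. An assessment by physical exam alone cannot be CR. CRu and CRi are not counted as CR and are tabulated separately.

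Keep the exam substitution for PR and routine follow-up. Add a sensitivity analysis that includes exam-only cases. Reconcile sections 7.0 and 9.1 to one IWCLL version and, in doing so, state whether the blood-count criteria apply to transfused or growth-factor-supported values.

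**Cost.** No new procedure is needed, since CT and marrow are already scheduled after cycle 6. The text does add a missing-data rule, and planned power has no slack: it falls to 76.5% or 72.4% if 5% or 10% of true CRs lack CT (assumed rates). Obtaining the scan within the window limits that loss.
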